8.3 Disposition of patients

A flow chart will be generated that shows the total population enrolled for this pragmatic randomized clinical trial, with the number of individuals assigned to the messaging intervention arm and the number of people assigned to the non-messaging arm. In each arm, we will describe the response count and rates to the:

- Baseline survey
- 3-month survey, and
- 6-month survey

8.4 Demographics and Baseline characteristics

Descriptive statistics (e.g., mean, standard deviation, frequency and percentage) of study participants will be reported for demographic variables (e.g., age, gender, education, income) and patient reported outcomes (e.g., vaccination rates). To confirm that block randomization is successful, we will compare the intervention to control groups in terms of baseline demographics, vaccine drivers/barriers, and vaccine knowledge for each of the block groups described earlier.

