A set of existing Achievement members who have previously self-reported to meeting the inclusion criteria will be tagged for study inclusion, termed "participants" from here on. Since participants will be blinded to their study participation status, participants will not be asked to take any action to enroll in the study. In order to identify a target list of participants, Evidation Health will leverage already permissioned information from Achievement members, including data on their cardiovascular diagnoses, age, sex/gender, race/ethnicity, and country of residence. These participants will be randomized using block randomization into CVD-Intervention or CVD-Control prior to being offered the opportunity to complete any study activities. Randomization will ensure that the groups are representative of the general Achievement population with cardiovascular disease. Efforts will be made to target individuals for enrollment who identify as being of a race/ethnicity that is something other than non-Hispanic White, as well as representative in sex/gender. Participants will be sent offers via the Achievement platform to complete study activities. Participants can complete any number of survey activities (demographics,

[figure not shown]
baseline, 3-month survey, and/or 6-month survey, intervention messages); completion of intervention activities will not be required for enrollment for the CVD-I group.

Study Steps

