Participants will be sent an offer to complete a survey at baseline, 3 months, and 6 months, and a demographic and medical history survey will remain available for participants to complete throughout the study. Additional information on study experiences and intervention feedback will be gathered in the 6-month survey for those in the CVD-I group. Data from an activity tracker will be collected if one is already connected to the participant's Achievement account, consistent with their completion of the Data Usage & Permissions Agreement. Activity tracker data will be collected retrospectively and prospectively. Participants in the CVD-I arm only will be sent intervention messages on predetermined days for the duration of the 6-month study intervention period. At the end of the intervention period, individuals who completed a data usage and permissions agreement as a part of the surveys will be informed via email that the survey information they contributed was for a research study investigating influenza vaccination behavior in people with cardiovascular conditions.

Study Compliance

Evidation study staff will track whether participants are completing study-related tasks throughout the study. Participants who do not complete study activities may be contacted by email, text message, or push notifications with reminders to complete activities, within a time window that is appropriate to the specific task, but will remain in the study sample regardless of whether they submit data in a timely manner.

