7.1 Derived Data

Cardiovascular condition type will be one of the following for the purposes of the secondary analysis objectives:

- People with self-reported arrhythmia only (not including atrial fibrillation)
- People with self-reported atrial fibrillation only
- People with self-reported heart attack, cardiac arrest or coronary artery disease only
- People with self-reported congestive heart failure only
- People with self reported stroke only
- People with two or more of the above conditions
- People with other cardiovascular conditions

Vaccine drivers and barriers of interest include:

- Number of visits to a primary care provider in the 3 months prior (categorized as None, 1-2, 3 or more)
- Number of visits to a cardiology specialist in the 3 months prior (categorized as None, 1-2, 3 or more)
- Hospitalization in the 3 months prior (categorized as none, once, 2 or more)
- Offered influenza vaccination by a healthcare provider (categorized as Yes, No, Unsure)
- Healthcare provider informed individual they were in a 'high risk group' (categorized as Yes, No, Unsure)

Vaccine knowledge factors are based on responses to the survey question "What sources of information do you use to learn about the flu vaccine?", with possible responses:

- Healthcare Professionals
- Family member or peers
- Social media including blog posts
- Mobile applications
- Conventional news media (e.g. television, newspapers)

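### The SAP 8.4 check on randomisation compares survey respondents after allocation, so it cannot separate chance imbalance from selective response; profile data held before allocation could check it

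*SAP*

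**What the plan says.** SAP 8.4 gives the purpose and the variables: "To confirm that block randomization is successful, we will compare the intervention to control groups in terms of baseline demographics, vaccine drivers/barriers, and vaccine knowledge". The comparison is to be made within block groups that the SAP says it has already described; neither document describes any. Protocol 8.2.1 has the same text.

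On timing, SAP 5 says: "These participants will be randomized using block randomization into CVD-Intervention or CVD-Control prior to being offered the opportunity to complete any study activities". On participation: "Participants can complete any number of survey activities". On the source of demographics: "a demographic and medical history survey will remain available for participants to complete throughout the study". On exposure in the same period: "Participants in the CVD-I arm only will be sent intervention messages on predetermined days for the duration of the 6-month study intervention period".

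The schedule in SAP 7 gives a survey as the source of demographics (the demographics survey) and of drivers and barriers (baseline, month 3 and month 6). SAP 7.1 bases vaccine knowledge on one survey question, "What sources of information do you use to learn about the flu vaccine", without saying which survey carries it.

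Some data were held on listed members before allocation. SAP 5 says the target list is built from profile information, "including data on their cardiovascular diagnoses, age, sex/gender, race/ethnicity, and country of residence". No comparison of all randomised members on these fields is planned.

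SAP 8.5 reports the relative rate on the assumption that the arms do not differ significantly in demographics, drivers/barriers or knowledge. It does not say what is reported if they do.

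**The concern.** A check on randomisation should use characteristics fixed before allocation, in everyone allocated. This one uses answers given after allocation by the minority who chose to respond. Two errors can follow.

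- **False alarm.** Sound randomisation can look faulty because different kinds of people answered in the two arms. Under SAP 8.5 this bears on whether the relative rate is reported.
- **False reassurance.** Balance among respondents says little about how the full list was allocated.

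The check also cannot tell an allocation fault from differential response. Differential response deserves the closer look here, because the primary population (P1, SAP 8.2) consists of people who answered the 3-month or 6-month survey.

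**Working it through.** **Inputs.** About 49,000 listed, 16% completion, about 8,000 analysed, and 7% completion in an internal survey of people with cardiovascular disease (all SAP 4). 1:1 allocation (SAP 4). Two-sided 5% tests (SAP 8.1).

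**The plan's own figure.** 49,000 × 0.16 = 7,840, which agrees with about 8,000 (8,000 / 49,000 = 16.3%). So 49,000 − 7,840 = 41,160 randomised people (84%) would be outside the check. At 7%, 49,000 × 0.07 = 3,430 respond and 93% are outside. The plan gives no completion figure for the baseline or demographic survey, so 16% and 7% serve here as an assumed range.

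**Can sound randomisation fail the check?** Assumptions: a binary covariate with true prevalence 50% in both arms; 24,500 per arm; equal overall response in both arms; response in CVD-C unrelated to the covariate; response in CVD-I higher by d in people with the covariate than in people without it.

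Prevalence among CVD-I respondents is p₁ = r₊ / (r₊ + r₋), where r₊ and r₋ are the response rates with and without the covariate. Among CVD-C respondents it is 0.5. With n respondents per arm, the test statistic is centred at (p₁ − 0.5) / √(2p̄(1 − p̄)/n), where p̄ is the pooled prevalence.

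Worked case, 16% response and d = 1 point:
- n = 24,500 × 0.16 = 3,920
- p₁ = 0.165 / 0.320 = 0.5156
- standard error ≈ 0.0113, so the centre is 0.0156 / 0.0113 ≈ 1.38
- P(significant) ≈ Φ(1.38 − 1.96) + Φ(−1.38 − 1.96) ≈ 0.28

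| d in CVD-I | 16% response (3,920 per arm) | 7% response (1,715 per arm) |
|---|---|---|
| 0 | 5% | 5% |
| 0.5 points | 11% | 18% |
| 1 point | 28% | 55% |
| 2 points | 79% | 99% |

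The same test on a pre-allocation field in all 49,000 stays at 5%, whatever the response pattern.

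**Can the check find a real imbalance?** The difference detectable with 80% power for a 50% covariate is (1.960 + 0.842) × √(0.5/n). This is 1.3 points with 24,500 per arm, 3.2 points with 3,920 and 4.8 points with 1,715.

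**The condition in SAP 8.5.** SAP 7.1 lists five drivers/barriers and five information sources. If each is tested once at 5% and the tests are independent, the chance of at least one significant result is 1 − 0.95¹⁰ = 40%, even with sound randomisation and no selective response.

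**The case against.** Several points on the other side stand in part.

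- **Source.** SAP 8.4 does not name its data source. Age and gender, two of its four example demographics, are also profile fields. That the check rests on surveys is inferred from sections 7 and 7.1; it is the natural reading, since education, income, drivers and knowledge are not among the listed profile fields.
- **Existing safeguards.** SAP 8.3 reports response to each survey by arm, and SAP 8.1 examines whether missing survey data are related to baseline characteristics. These partly cover differential response. Neither is linked to the balance check, and the missingness analysis is not specified by arm.
- **Usefulness.** The primary analysis uses respondents, so comparing respondents by arm is worth doing. The faults are its label and the weight it carries in SAP 8.5. The adjusted logistic model is not subject to that condition.
- **The alternative check.** If blocks were formed on profile fields, those fields would balance largely by design and comparing them would show little. Completeness of sex/gender and race/ethnicity is not stated. Non-respondents do not reach the data-use agreement that opens each questionnaire (Protocol 6.2), and the documents do not settle whether their profile data may be analysed beyond targeting.

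A reader might infer that the messages contaminate the baseline survey, for instance by raising the share naming mobile applications as an information source. The documents do not establish this. The available text does not say whether the baseline survey precedes the first message, and the flow diagram is not reproduced. Messages cannot change age or education, and three of the five drivers look back over the preceding 3 months. A message effect is possible only if answers given after the first message are used. That could happen for P1 members with no baseline survey, but the plan does not say so.

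**Conclusion.** The point holds in a limited form: the comparison in SAP 8.4 cannot confirm randomisation, because it mixes chance imbalance with selective response. It would be too strong to say that it tests response or message effects in place of randomisation; chance imbalance is still part of what it measures. Nothing in the documents suggests that allocation itself is faulty.

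The size depends on how response varies, which the plan does not forecast. The 28% and 79% figures rest on a 50% covariate, 16% overall response in both arms, and a 1- or 2-point response difference by covariate in CVD-I only. With no such difference, a single test keeps its 5% error rate.

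The practical consequence is in SAP 8.5, where a false alarm could affect how the primary result is reported. The fault is worth correcting and does not undermine the design.

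**What to change.** 1. **SAP 8.4, allocation.** Compare all randomised participants by arm on the profile fields held before allocation (cardiovascular diagnosis, age, sex/gender, race/ethnicity), and report the completeness of each. State the block factors, so the reader can see which fields balance by design, or remove the reference to block groups.
2. **SAP 8.4, respondents.** Present survey demographics, drivers/barriers and information sources by arm as a comparison of respondents, using baseline answers submitted before the first message date. Show beside it response by arm and by profile characteristic, extending SAP 8.1 and 8.3. Do not cite it as evidence about randomisation.
3. **SAP 8.5.** Report the relative rate regardless of that comparison. Editing 8.4 alone would leave the condition in force.
4. **SAP 6.** Record the departure from Protocol 8.2.1 and 8.2.2, which carry the same wording.

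The cost is SAP wording and one or two tables from data already held, with no new collection. Profile completeness may limit some fields, and the sponsor should confirm that existing permissions allow non-respondents' profile data to be tabulated.

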8.5 Primary objective analysis

An intention to treat analysis will be conducted of the primary outcomes for the study. Assuming that a descriptive comparison of the intervention to the control group does not demonstrate statistically significant differences in terms of demographics, vaccine drivers/barriers, or vaccine knowledge, we will report on the relative rate of influenza vaccination for the intervention group compared to the control group. This is given simply by:

RR = rate of influenza vaccination among intervention group rate of influenza vaccination among control group

We will also conduct logistic regression modeling of influenza vaccination as follows:

$$logit(Y) = \beta_0 + \beta_1 M + \sum_i \beta_i \alpha_i + \varepsilon$$

Where:

logit(Y) = ln(Y/1-Y) for the binary variable designation of influenza vaccination status M = the binary designation for Intervention (messaging) vs Control (no messaging) $\alpha_j = the$ baseline covariates measured in the study (e.g. demographics, vaccine drivers/barriers or knowledge) $\epsilon = the$ error term of the regression.

Vaccine drivers and barriers are described above in Section 8.1: Derived Variables

For the logistic regression model the p-values, odds ratio and associated 95% CI associated with each of the β parameter estimates will be reported.

Kaplan-Meier curves will be constructed for time-to-influenza vaccination, using the participant estimated dates of influenza vaccination from the 3 and 6 month surveys.

- 8.6 Secondary objective analysis
- 8.6.1 To examine predictors of vaccination status, including cardiovascular condition type, vaccine drivers/barriers, and vaccine knowledge, across and between CVD-I and CVD-C.

To examine predictors of vaccination status, including cardiovascular condition type, vaccine drivers/barriers, and vaccine knowledge, across CVD-I and CVD-C we will construct the model:

$$logit(Y) = \beta_0 + \sum_i \beta_i P_i + \sum_i \beta_i \alpha_i + \varepsilon$$

Where:

logit(Y) = ln(Y/1-Y) for the binary variable designation of influenza vaccination status P_i = the predictor of interest i (e.g. cardiovascular condition, vaccine drivers/barriers, vaccine knowledge) α_j = the baseline demographics ϵ = the error term of the regression.

Cardiovascular condition type is described above in Section 8.1: Derived Data. Vaccine drivers and barriers are described above in Section 8.1: Derived Variables. The beta-parameter estimates, p-values, adjusted odds ratio and 95% CI will be reported. SHapley Additive exPlanations (SHAP) values will be used to assess the individual contributions of each predictor variable [Lundberg, 2017].

To describe the predictors of vaccination status and how it varies between CVD-I and CVD-C, we will use the model:

$$logit(Y) = \beta_0 + \beta_1 P + \beta_2 C + \sum_i \beta_i P_i * C + \sum_i \beta_i \alpha_i + \varepsilon$$

Where the variable *C* is a binary (1,0) designation for CVD-I and CVD-C respectively, and the beta-estimate for interaction term will be reported with the corresponding p-value, adjusted odds ratio and 95% CI. As with above, the SHAP values will be used to evaluate the individual contributions of each predictor variable.

People who report getting the influenza vaccination are asked a series of behavioral and attitudinal questions around where, how and when the vaccination was received. Those survey responses will be summarized for the study population. Similarly, people who did not obtain an influenza vaccine are asked a set of questions around attitudes and willingness to vaccinate, and those will also be summarized. Changes in response to questions on vaccine drivers and barriers will be examined between the baseline survey and the final survey.

8.6.2 To describe engagement with interventions, including clicking, opening, or completing the intervention messages

To examine differences in vaccination rates between individuals in the CVD-I group and its relationship to engagement with intervention messages, we will model:

$$logit(Y) = \beta_0 + \beta_1 M + \sum_i \beta_i \alpha_i + \varepsilon$$

Where:

logit(Y) = In(Y/1-Y) for the binary variable designation of influenza vaccination status M = the number of engaged messages (ordinal variable 0, 1, 2, 3, 4, 5, 6) α_i = the baseline covariates measured in the study (e.g. demographics, CVD type)

- 8.7 Exploratory objective analysis
- 8.7.1 To describe the self-reported impact of the COVID-19 pandemic on influenza vaccination behavior Descriptive summaries of the participant responses to the monthly survey questions on COVID-19 will be

provided.

8.7.2 To examine differences in wearable data (i.e., sleep, steps, heart rate) between individuals who experience influenza and those who do not, as well as differences in wearable data between cardiovascular conditions.

Participants are asked if they were diagnosed with influenza infection in the preceding 3 months for the 3-month and 6-month survey. Differences in daily steps per day, total sleep hours and resting heart rate will be aggregated over the 3 month period and compared among people who report having influenza to those who do not. Similar comparisons within each type of cardiovascular condition will also be performed.

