Based on this, we believe that a 3% effect size is a reasonable assumption and that a sample size of approximately 8,000 participants will be needed to detect this difference with a type I error rate of 0.05 and a presumed power of 0.80. A participation drop-off of 67% has been observed for digital interventions for increasing influenza vaccination in people with diabetes (i.e., Samson et al., 2020). A recent internal survey of individuals with cardiovascular disease demonstrated a survey completion rate of approximately 7%, indicating that this population may have lower than expected engagement. Based on these calculations, we plan to recruit approximately 49,000 participants, anticipating that on average, engagement may be approximately 16%. A targeted enrollment list of approximately 49,000 individuals with 16% survey completion would reach the estimated analysis population of 8,000 participants needed.

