8 STATISTICAL METHODS

8.1 General Statistical Approaches

For the study variables, we will perform distributional analysis. When describing the study population, we will use min, max, mean, and standard deviations for continuous variables (i.e. age, BMI) and frequency counts for categorical variables (i.e. gender, ethnicity). For both continuous and categorical variables, we will report on the number of participants evaluated for that variable, as well as the number of people with non-missing values. For the study variables, we will also look at individual-level rates of missing data. Missing data or unknown responses will be described separately and not be counted in the summary descriptions of the variables. We will report on the percent of missing data for each of the included data sources (surveys, activity data) and evaluate whether any missingness is associated with baseline participant-level characteristics in the case of missing survey data or with the outcome in the case of activity tracker data.

Statistical testing comparing variables will be performed at the 5% significance level using two-sided tests or two-sided 95% confidence intervals (CI), unless otherwise specified. Comparison of means will use Student's t-test for normal distributions, or a Mann-Whitney U test for non-normal distributions. Comparisons of frequencies will use chi-square tests. Regression modeling approaches are described below. We will report on the size of the beta-parameter estimate and the associated significance level (p-value) for each predictor variable.

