8.2 Analysis Population (s)

The analysis populations will consist of:

- P1: This population will consist of all individuals who respond to the 3-month or 6-month survey. It will
 be used for the primary objective analysis and for the first part of the secondary objective (examine
 predictors of vaccination status across the CVD-I and CVD-C arms). This population will also be used
 for the second exploratory objective, which is to describe self-reported complications from influenza
 during the study period.
- P2: This population will consist of all individuals who are in the CVD-I arm and have responded to the 3-month or 6-month survey. It will be used for the second part of the secondary objective, which is to describe the engagement with different intervention messages and its relationship to influenza vaccination status.
- P3a: This population will consist of individuals who responded to the baseline, 3-month or 6-month survey. It will be used to examine the first part of the exploratory objectives - specifically the selfreported impact of COVID-19 on influenza vaccination and behavior.
- P3b: This population will consist of all individuals who complete either the 3-month or the 6-month survey, who have wearable activity data and who consent in the final (6-month) survey to have the activity data analyzed for this study. This population will be used for the 3rd exploratory objective, specifically to explore the differences in wearable data (i.e., sleep, steps, heart rate) between individuals who experience influenza and those who do not, as well as differences in wearable data between cardiovascular conditions.

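### The primary analysis is called intention to treat but covers only survey responders, planned at about 16% of those randomised, with no sensitivity analysis for response that depends on vaccination

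*SAP*

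**What the plan says.** SAP 8.5: "An intention to treat analysis will be conducted of the primary outcomes for the study". Protocol 8.2.2 makes the same statement.

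SAP 8.2 defines P1: "This population will consist of all individuals who respond to the 3-month or 6-month survey". It says that P1 will "be used for the primary objective analysis". The other populations (P2, P3a, P3b) are also limited to survey responders, so none contains everyone randomised. Yet SAP 5 (Study Compliance) keeps people who do not complete activities in the study sample.

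SAP 5 (Recruitment Methods) places randomisation "prior to being offered the opportunity to complete any study activities". SAP 4 plans a list of about 49,000, which "with 16% survey completion would reach the estimated analysis population of 8,000 participants needed". It gives this next to a 7% completion rate from an internal survey and a 67% drop-off in an earlier diabetes study.

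The plan does look at response:

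- SAP 8.3: "In each arm, we will describe the response count and rates to the" baseline, 3-month and 6-month surveys.
- SAP 8.1: the team will "evaluate whether any missingness is associated with baseline participant-level characteristics in the case of missing survey data".
- The logistic model in SAP 8.5 adjusts for baseline covariates.

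Neither document plans imputation, weighting, bounds or a tipping-point analysis.

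**The concern.** Intention to treat tells a reader that the comparison is protected by randomisation and applies to everyone randomised. A comparison restricted to people who later chose to answer a survey has neither property. The outcome is self-reported in those same surveys, so the decision to respond may be related to the outcome.

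The bias that matters is arm-specific: vaccinated people being relatively more or less likely to respond in one arm than in the other. The arms are contacted differently, since "Participants in the CVD-I arm only will be sent intervention messages on predetermined days", and the messages concern the outcome being reported. The target effect is only 3 points. Selection of that kind could create a difference of that size or hide a real one, and the result would still be reported as intention to treat.

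**Working it through.** **The plan's own figures**

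- Analysed: 49,000 × 0.16 = 7,840, close to the stated 8,000. Not analysed: 49,000 − 7,840 = 41,160 (84%).
- Sample size for 50% vs 53%: the arcsine formula gives 4,355.3 per arm, or 8,712 after doubling and rounding up to an even number. The table states 8,710.

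**Inputs**

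- From the SAP: about 49,000 randomised 1:1, so 24,500 per arm; 16% response; two-sided 5% test; 3-point target; 50% as one of the planning vaccination rates.
- Assumed: the response rates by vaccination status. The documents give none, so the cases below show size and not likelihood.

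**Formula**

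If p is the true vaccination rate in an arm, and r1 and r0 are the response rates of vaccinated and unvaccinated people, the rate seen among responders is p·r1 / (p·r1 + (1 − p)·r0).

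**No true effect, 50% vaccinated in both arms, control response 16% throughout**

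| CVD-I response, vaccinated / unvaccinated | Responders, CVD-I / CVD-C | Observed CVD-I rate | False difference | z | Chance of p<0.05 | Overall response, CVD-I vs CVD-C |
|---|---|---|---|---|---|---|
| 18% / 16% | 4,165 / 3,920 | 0.18/0.34 = 52.9% | +2.9 points | 2.65 | 75% | 17% vs 16% |
| 17% / 16% | 4,042 / 3,920 | 0.17/0.33 = 51.5% | +1.5 points | 1.35 | 27% | 16.5% vs 16% |
| 17% / 15% | 3,920 / 3,920 | 0.17/0.32 = 53.1% | +3.1 points | 2.77 | 79% | 16% vs 16% |

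Would the response rates in SAP 8.3 reveal this? A test of overall response would have about 85% power in the first case and 32% in the second, but no such test is planned. In the third case, which needs exact offsetting, overall response is equal and the rates show nothing.

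**Other response levels**

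The false difference in the first case depends only on the 18:16 ratio. It stays at +2.9 points with 7% control response (z = 1.75, p<0.05 about 42% of the time) and with 33%, that is 1 − 0.67 (z = 3.80, about 97%).

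**Hiding a true effect**

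With true rates of 53% vs 50% and the ratio reversed in CVD-I (16% vaccinated, 18% unvaccinated), the observed CVD-I rate is 0.53 × 0.16 / (0.53 × 0.16 + 0.47 × 0.18) = 0.0848/0.1694 = 50.1%, against 50.0% in CVD-C.

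**Tipping point**

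Suppose responders show 53% vs 50% and response r is equal in both arms. The all-randomised difference is r·3 + (1 − r)·d, where d is the CVD-I minus CVD-C difference among non-responders, in points. Setting it to zero gives d = −3r/(1 − r):

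- r = 0.07: −0.23
- r = 0.16: −0.57
- r = 0.33: −1.48

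At r = 0.16 the standard error is √(0.53 × 0.47/3,920 + 0.50 × 0.50/3,920) = 1.128 points, so the lower 95% limit is 3 − 1.96 × 1.128 = 0.79. Holding the imputed rates fixed, the all-randomised interval first includes zero at d = −0.16 × 0.79/0.84 = −0.15 points.

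**The case against.** Several points can be made for the plan.

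- **The label may mean analysed as assigned, whatever the engagement with messages.** SAP 5 does say that completing intervention activities is not required. That reading deals with engagement. It does not deal with selection into the outcome data.
- **P1 is openly defined, and a flow chart will show assignment and response by arm.** True, so a careful reader could work out what was done. The label would still be wrong.
- **Response that depends on vaccination does not always bias the result.** This stands. If vaccinated people respond 1.5 times as often in both arms, 53% vs 50% becomes 0.795/1.265 = 62.9% vs 60.0%, and the odds ratio stays at 1.128. SAP 8.5 also reports a relative rate, however, and that moves from 53/50 = 1.06 to 62.9/60.0 = 1.05. The serious bias needs an arm-specific ratio.
- **Nothing shows that arm-specific selection is likely.** This also stands. Both arms are paid for surveys (Protocol 6.5), and reminders to non-completers are not limited to one arm (SAP 5). The response rates used above are assumptions.
- **The tipping point is not one number when response differs by arm.** Correct. With 17% vs 16% response and responders at 53% vs 50%, the zero point is −0.86, −0.61 or −0.37 points when control non-responders are vaccinated at 30%, 50% or 70%. The analysis should therefore be reported as a grid.

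These points limit what can be said about likelihood and shape the remedy. None removes the contradiction or supplies the missing analysis.

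**Conclusion.** The concern holds. The intention-to-treat label in SAP 8.5 and Protocol 8.2.2 cannot stand beside the responder-only population in SAP 8.2. This concerns the primary analysis and should be corrected before it is run.

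The planned checks on response and the covariate adjustment do not protect against vaccination-dependent response that differs by arm. Under the stated assumptions, a 2-point shift in response in one subgroup of one arm produces +2.9 of the 3 target points with no true effect. A non-responder difference of −0.57 points cancels an observed 3-point effect at 16% response in both arms. How likely such selection is cannot be judged from the documents, so the plan needs a way to show how robust its result is.

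**What to change.** 1. **Relabel.** In SAP 8.5, describe the primary analysis as an analysis of survey responders (P1) by randomised arm, and carry that wording into the conclusion. Make the same change in Protocol 8.2.2, or record the departure in SAP 6.
2. **Pre-specify a tipping-point analysis over all randomised participants.** Vary the non-responders' vaccination rate separately in each arm on a two-way grid. For each control rate, report the between-arm difference among non-responders at which the estimate reaches zero, and the one at which the 95% interval first includes zero.
3. **Optional: response weights fitted by arm.** The profile data on age, sex/gender, race/ethnicity and cardiovascular diagnosis that SAP 5 uses to build the target list could serve. State that the weights address only response explained by those covariates. If response depends on vaccination itself, as in the cases above, they would leave the bias in place.

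**Cost.** Wording changes and a few extra analyses on data already held, with no new collection. The claim becomes less favourable, since it applies among survey responders. At 16% response the tipping thresholds will be small, so any conclusion about everyone randomised will have to be cautious.
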